8.2.7 Visit 11 (65 week) - Follow-up

Please note that the patient should fast for 8-12 hours before attending the visit.

- Physical examination, weight and waist circumference.
- Vital signs including sitting blood pressure, heart rate, respiratory rate and body temperature.
- Blood sample for Aramchol blood trough level. (only in Israel-the patients will be asked to take the daily tablet at the clinic after blood sample are taken and to record the time).
- Concomitant medication.
- Adverse Events that occurred since the last visit will be recorded.
- Safety laboratory assessments: Chemistry Hematology, ESR, Coagulation and Urinalysis.
- Lifestyle changes (including importance of diet and exercise in weight management). Life style Questionnaire (appendix E) may be used as a guideline, but is not mandatory.

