	The subjects will be evaluated at study sites for 11 scheduled visits: at screening (visit 1(weeks $-4 - 0$)), baseline (visit 2 (day 0)), visit 3 (week 2), visit 4 (week 4), visit 5 (week 8), visit 6 (week 12), visit 7 (week 24), visit 8 (week 32), visit 9 (week 40) and visit 10 (week 52 End-of-Treatment/Early Termination visit). After completion of the study treatment period, the subjects will be followed for an additional period of 13 weeks without study medication until visit 11 (week 65).
	 During the screening period, the severity of the disease will be evaluated with blood tests, liver biopsy and NMRS. During the study the following assessments will be performed: Vital signs will be measured at each study visit. A physical examination will be performed at the screening visit, 24 weeks, End-of-Treatment/Early Termination and week 65 visit. The following blood tests will be performed: complete blood count (CBC), serum chemistry (including electrolytes, liver enzymes, direct and total bilirubin, glucose, lipid profile which include triglyceride, cholesterol, HDL, LDL and VLDL, CPK, creatinine, urea, albumin, alkaline phosphatase), ESR and urinalysis during the screening visit, baseline, week 2, 4, 8, 24, 40, 52 and 65 (end of follow up) visits. Serology (HBV, HCV and HIV) will be performed during the screening visit. Coagulation (fibrinogen, PT/INR, aPTT) will be measured at screening and baseline, week 24 and End-of-Treatment/Early Termination visits. HbA1C will be measured at the screening, week 8, 24, 40 and End-of-Treatment/Early Termination visits. C reactive protein, Leptin, Adiponectin,
	will be measured at the baseline visit and end of treatment period. The blood samples taken at these visits, will be tested for possible biomarkers. TSH, T3 and T4 will be measured during the screening visit. β -hCG in women of childbearing potential will be performed during the screening visit. A serum sample will be collected and kept frozen until study end in case special investigation needs to be performed. This sample will be collected during the screening and visit 10/Early Termination.

	- Body weight and waist circumference will be measured at
	screening, baseline, week 24, end of treatment and week 65 visits.
	Height will be measured during the screening visit.
	- ECG will be performed during the screening visit, visit 7 (week 24)
	and End of Treatment/Early Termination visit.
	- All subjects will undergo two NMRS scans, at screening and end of

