5 STUDY DESIGN

5.1 Over view and plan

This is a multicenter, phase IIb, randomized, double blind, placebo controlled study designed to evaluate the efficacy and safety of two Aramchol doses (400 mg and 600 mg) in subjects that

are 18 to 75 years of age, with Non-Alcoholic Steatohepatitis (NASH) and type II DM or elevated fasting glucose and overweight/obesity (type II diabetic or pre diabetic). Eligible subjects will be enrolled in three treatments arms:

- Aramchol 400 mg tablets
- Aramchol 600 mg tablets
- Placebo for Aramchol

The subjects will be evaluated at study sites for 11 scheduled visits: visit 1 (screening), visit 2 (baseline), visit 3 (2 weeks), visit 4 (4 weeks), visit 5 (8 weeks), visit 6 (12 weeks), visit 7 (24 weeks), visit 8 (32 weeks), visit 9 (40 weeks), visit 10 (End-of-Treatment/Early Termination) (52 weeks) and visit 11 (follow up) (65 weeks).

The subjects will be treated for a period of 52 weeks. After completion of the study treatment period, the subjects will be followed up for an additional period of 13 weeks without study medication

During the study the following assessments will be performed:

- Vital signs will be measured at each study visit.
- A physical examination will be performed at the screening visit, 24 weeks, End-of-Treatment/Early Termination and week 65 visits.
- The following safety blood tests will be performed: complete blood count (CBC), serum chemistry (including electrolytes, liver enzymes, direct and total bilirubin, glucose, lipid profile which include triglyceride, cholesterol, HDL, LDL and VLDL, CPK, creatinine, urea, albumin, alkaline phosphatase), ESR and during the screening visit, baseline, week 2, 4, 8, 24, 40, 52 and 65 (end of follow up) visits. Serology (HBV, HCV and HIV) and urinalysis will be performed during the screening visit. Coagulation (fibrinogen, PT/INR, aPTT) will be performed during the screening, baseline, week 24, End-of-Treatment/Early Termination and week 65 visits. Insulin (HOMA) will be measured in the screening, week 24 and End-of-Treatment/Early Termination visits. HbA1c will be measured in the screening, week 8, 24, 40 and End-of-Treatment/Early Termination visits. C reactive protein, Leptin, Adiponectin,

will be measured in baseline visit and end of treatment period (week 52, visit 10). The blood samples taken at these visits, will be tested for possible biomarkers

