8 STUDY CONDUCT

8.1 Study Period

The study assessments will be performed according to the summary of the Visit Schedule and Assessments (see table 1).

A month in the treatment period is defined as 28 days \pm 7 days.

The study period consists of the following phases:

Screening period: up to 4 weeks. In case of delay in NMRS scans performed and/or

interpretation, screening period may be extended up to 45 days.

Double blind treatment period (treatment phase): 52 weeks of once-daily oral administration of Aramchol 400 mg/day or 600 mg/day or matching placebo.

Follow up period: 13 weeks after end of active treatment, without study medication.

Protocol No: 005 ARREST study

CONFIDENTIAL *Final*

Table 1 – Visit schedule and Assessments

	Week	-4 to 0 weeks	0 day 1	2	4	8	12	16&20	24	28	32	36	40	44 & 48	52	65	Un schedu led
$ \begin{array}{ c c c c c c c c c c c c c c c c c c c$		trial														F/U	
Informed Consent N	Visit N°	1	2	3	4	5	6	T1&2	7	Т3	8	T4	9		10	11	
	Informed Consent	Х												•			
			Х														
Medical History X Image of the second seco		Х															
Current Disease Status X																	
Viral Signs X <t< td="">	Х																</t<>		Х															
Viai X Physical examination								Х						Х	Х	Х	Physical examination								Х						Х	Х	Х
		Х	Х	Х	Х	Х	Х		Х		Х		Х		Х	Х	Х
$\begin{array}{c c c c c c c c c c c c c c c c c c c $		Х	Х						Х						Х	Х	Х
$\begin{array}{c c c c c c c c c c c c c c c c c c c $	Height	Х															
$\begin{array}{ c c c c c c c c c c c c c c c c c c c$																	
$\begin{array}{c c c c c c c c c c c c c c c c c c c $	Waist circumference	Х	Х						Х						Х	Х	Х
$\begin{array}{c c c c c c c c c c c c c c c c c c c $	Imaging - NMRS	Х													Х		
$\begin{array}{c c c c c c c c c c c c c c c c c c c $									Х								Х
$\begin{array}{c c c c c c c c c c c c c c c c c c c $	Liver Biopsy																
$\begin{array}{c c c c c c c c c c c c c c c c c c c $		Х	Х	X ⁷	X7	X7			Х				X7		Х	Х	Х
$\begin{array}{c c c c c c c c c c c c c c c c c c c $	Coagulation ⁶	Х	Х						Х						Х	Х	[
$\begin{array}{c c c c c c c c c c c c c c c c c c c $	ESR ⁸			X8	X8	X8			X8				X8		X8		X ⁸

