8.2.6 Visit 10 (week 52) – End of treatment /Early Termination

Please note that the patient should fast for 8-12 hours before attending the visit. If the patient is taking any anticoagulant it should be stopped sufficient time before biopsy is taken. Taking NSAIDs should be prohibited 48 hours prior to conducting biopsy

- Physical examination.
- Vital signs including sitting blood pressure, heart rate, respiratory rate and temperature.
- Measuring body weight and waist circumference.
- Safety laboratory assessments: Chemistry Hematology, ESR, Coagulation and Urinalysis. Please note that Coagulation results should be within normal ranges before Biopsy performed.
- Blood samples for insulin (HOMA).
- Blood samples for Adiponectin, Leptin,

. The blood samples

taken at these visits, will be tested for possible biomarkers

- Serum blood sample will be collected and kept frozen in case special test to clarify safety issue will be required and in case special investigation will be needed to be performed.
- HbA1c.
- Endothelial Function. This test will be conducted at selected sites.
- ECG (12 leads) evaluation.
- Liver NMRS examination.

- Liver biopsy which should be reviewed by the recruiting investigator and confirmed by the study pathologist.
- Fatty liver index (FLI).
- Metabolomics blood tests (from all patients) as well as part of the liver biopsy (from approximately 15 patients, the same patients who had not revoked consent and samples collected from at the screening visit) will be taken for the test and kept frozen.
- NFS
- Recording of concomitant medication.
- Adverse Events that occurred since the last visit will be recorded.
- Lifestyle changes (including importance of diet and exercise in weight management. Life style Questionnaire (appendix E) may be used as a guideline, but is not mandatory .
- Blood sample for Aramchol blood trough level (only in Israel- The patients will be asked to take the daily tablet at the clinic after blood sample are taken and to record the time).
- Drug accountability.

MRI will be recommended to patients that completed at least 24 weeks in the study (visit 7). Biopsy will be recommended to patients that completed at least 40 weeks in the study (visit 9).

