9.8 Aramchol blood trough level

Blood samples for trough Aramchol blood level will be collected from subjects participating in the study in Israel at visits 2 (baseline), 4, 6, 7, 9, 10 and 11.

One blood sample will be collected on visit 4 or 9 at selected sites in Mexico, USA, Europe and Hong Kong to test for trough Aramchol blood level differences between populations (e.g., African American, Asian, Hispanic).

In these visits the subjects will be asked not to take the study medication before attending the visit at the clinic but only after the blood sample for trough Aramchol blood level will be taken. The date and time of the blood sample, as well as the date and time of the last study drug dose prior to the sample will be recorded on the e-CRF.

The blood samples will be collected and transferred into pre-labeled pre-chilled (ice-based water bath (4^oC)) EDTA-K2 tubes. Following each collection, the tube will be gently inverted several times to assure complete mixing with the potassium EDTA and should then be placed on ice pending centrifugation.

Plasma will be separated by centrifugation for 10 min within 45 minutes of collection at approximately 2000g (2600-3000 rpm) and +4°C. Deviations from the blood sampling times will be recorded in the appropriate eCRF. Plasma samples will be divided into duplicate labeled Cryotubes (at least 600 μ l per tube) by the site and sent frozen on dry ice to the central laboratory for storage at -70°C. Samples for blood trough levels evaluation will be sent periodically on dry ice to Analyst Research Laboratories, Rehovot, Israel. All shipments will be accompanied by a detailed sample inventory list, and the bio-analytical laboratory will be notified in advance by telephone, fax or e-mail before the shipment of study samples. Aramchol plasma concentrations will be determined using a validated LC-MS/MS method.

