12.9.1 Adverse Events

An adverse event is any untoward medical occurrence in a patient administered a pharmaceutical product, regardless of whether it has a causal relationship with this treatment. In this study, any adverse event occurring after the clinical study patient has signed the informed consent form should be recorded and reported as an adverse event.

The MedDRA dictionary Version 19 will be used to standardize the terms used by the investigator to describe the Adverse Events (AEs).

The following analyses are pre-planned for adverse events:

- The incidence (no. of patients) and frequency (no. of events) of most frequent TEAEs (>5% of subjects in at least one study arm) by Preferred Term.
- The incidence (no. of patients) and frequency (no. of events) of TEAEs when broken down by SOC and by SOC and Preferred Term according to MedDRA dictionary.
- The incidence (no. of patients) and frequency (no. of events) of TEAEs started during the off-drug study follow-up period (from week 52 to week 65) when broken down by SOC and by SOC and Preferred Term according to MedDRA dictionary.
- The incidence (no. of patients) and frequency (no. of events) of TEAEs by MedDRA System Organ Class and Preferred Term in Subjects Early Terminated from Study/Treatment.
- The incidence (no. of patients) and frequency (no. of events) of serious TEAEs by MedDRA System Organ Class and Preferred Term, data listing as well as summary table of SAEs when broken down by study trimesters (90 days each).
- The incidence (no. of patients) and frequency (no. of events) of TEAEs when broken down by severity.
- The incidence (no. of patients) and frequency (no. of events) of TEAEs when broken down by relationship to study IP.

- The incidence (no. of patients) and frequency (no. of events) of TEAEs when broken down by action taken.
- The incidence (no. of patients) and frequency (no. of events) of TEAEs when broken down by event outcome.
- Adverse Events dictionary used to code Investigator's verbatim terms will also be provided. Individual subject listings of TEAEs and non-TEAEs.

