12.9.6 Tolerability and Drop-Out Assessments

Tolerability analysis will be based on the number and percent (%) of subjects who failed to complete the 52 Weeks of the study by withdrawal reason will be presented. Time to withdrawal will also be presented by Kaplan-Meier curves.

Protocol No: 005 ARREST study

The number and percent (%) of subjects who failed to complete the entire study duration of 65 Weeks (52 weeks of double blind treatment and additional 13 weeks of double blind off study drug follow-up) will also be reported.

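### Section 8.2.7 tells Israeli patients to take the daily tablet at week 65, after 13 weeks off drug, and the same instruction in 8.2.6 does not exclude early-termination patients who have stopped treatment

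*Combined protocol and SAP*

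**What the plan says.** Section 8.2.7 covers Visit 11, the follow-up visit at week 65. Its bullet on the Aramchol trough level adds an instruction: "only in Israel-the patients will be asked to take the daily tablet at the clinic after blood sample are taken". Patients are also to record the time.

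Section 8.2.6 covers Visit 10, which is both the week 52 end-of-treatment visit and the early-termination visit. Its bullet reads "Blood sample for Aramchol blood trough level (only in Israel- The patients will be asked to take the daily tablet at the clinic", and it too places the tablet after the sample. It does not separate patients finishing treatment from patients who have stopped early.

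Section 9.8 lists the Israeli sampling visits as 2, 4, 6, 7, 9, 10 and 11. Of these visits it says that "subjects will be asked not to take the study medication before attending the visit at the clinic but only after the blood sample" has been drawn. Footnote 3 of Table 1 likewise places the sample ahead of that day's dose.

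Five places describe weeks 52 to 65 as off drug:
- Synopsis: "followed for an additional period of 13 weeks without study medication until visit 11 (week 65"
- Section 5.1: "followed up for an additional period of 13 weeks without study medication"
- Section 8.1: "13 weeks after end of active treatment, without study medication"
- Section 12.9.1: "started during the off-drug study follow-up period (from week 52 to week 65"
- Section 12.9.6: "additional 13 weeks of double blind off study drug follow-up"

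**The concern.** The bullets in 8.2.6 and 8.2.7 are visit instructions that site staff follow. Read literally, 8.2.7 has a patient who finished treatment three months earlier take one more dose, after which the protocol schedules no further visit.

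The early-termination half of 8.2.6 matters more. Section 8.4 requires that visit of randomized patients who discontinue study drug early. The reasons in 8.4.1 include adverse events, grade III or IV toxicity that persists or recurs, and pregnancy. Under 8.6.8 patients bring unused tablets back at each visit, so tablets may be in the room when the instruction is read. What is at stake is an unintended dose in a patient who should be off drug. The trial's inference is not at stake.

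**Working it through.** No sample size, power or error rate is involved. The check is the timeline, followed by a comparison of the sections.

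**Timeline.** Treatment lasts 52 weeks and follow-up 13 weeks (synopsis, 8.1). 52 + 13 = 65, which reproduces the stated week of Visit 11. 13 × 7 = 91, so Visit 11 is nominally 91 days after the scheduled end of treatment.

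**Sampling visits.** Section 9.8 lists seven for Israel: 2, 4, 6, 7, 9, 10 and 11.

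| Visits | Status of the patient | Is a tablet due after the sample? |
|---|---|---|
| 2, 4, 6, 7, 9 (five visits) | starting or on treatment | yes |
| 10, reached at week 52 on treatment | finishing treatment | acceptable |
| 10, used for early termination | study drug discontinued (8.4) | no |
| 11 | 13 weeks off drug | no |

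So the instruction is wrong for all Israeli patients at one of the seven visits, and wrong for the early-termination subgroup at one more. For patients still on treatment at Visit 10 it is not clearly an error, because 9.1 and 9.2 let the closing scan and biopsy fall up to 7 days after that visit.

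**Does another section settle it?**
- Visit 11: the five off-drug statements contradict the clause, but none mentions or withdraws it. Section 9.8 includes Visit 11 without an exemption.
- Early termination, pregnancy: sections 7.3 and 11.6 forbid any further dose. That conflicts with 8.2.6 as worded, although the intent is clear.
- Early termination, other reasons: 7.3 takes patients with hepatotoxicity off the study, and 8.4 keeps patients with ongoing adverse events or severe intolerance under observation. Neither says that the Visit 10 tablet is to be omitted.

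**Was dosing at Visit 11 intended?** Section 8.6.8 schedules kit dispensing at Visits 2 and 4 to 9, plus unscheduled visits as needed. Drug accountability is listed at Visit 10 and not at Visit 11. Both indicate that no tablet was meant to be taken at week 65.

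**The case against.** The strongest reply is that nobody would act on the clause. At Visit 11 the site has no scheduled supply, leftover tablets should already have been returned, and the protocol says five times that the patient is off drug. At early termination, a reference to the daily tablet presupposes a patient who still has one, and 7.3, 8.4 and 11.6 govern the patients of most concern. This stands as an argument about likelihood, and it is why the point ranks low. It does not make the text right: 8.2.7 is a complete, specific instruction that cannot be reconciled with the follow-up design, and 8.2.6 draws no line between the two groups it covers.

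A reader might infer more than the documents support:
- **That 9.8 also orders a dose at Visit 11.** It is a rule about sequence, and its purpose is to protect the trough measurement. Where no dose is due, nothing follows from it. The same holds for footnote 3 of Table 1. Both would be clearer with a limit, but neither is a dosing error.
- **That nothing in the protocol counters the early-termination instruction.** For pregnancy, 7.3 and 11.6 do so expressly. The gap concerns the other reasons for stopping.
- **That the Visit 11 clause was copied from Visit 10.** The wording is similar, but it also appears in 8.2.3 and 8.2.4, so its source cannot be known. The error does not depend on it.

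**Conclusion.** The point holds as a wording error in an operational instruction. The tablet clause in 8.2.7 contradicts the off-drug follow-up and is wrong for every patient to whom it applies. The clause in 8.2.6 is suitable for patients still on treatment at week 52. It is too broad for those attending after discontinuation, and for pregnancy it conflicts with a rule stated elsewhere in the protocol.

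The size is small. Only Israeli patients are affected, and the documents do not say how many there are or how many might terminate early. No kit is scheduled at Visit 10 or 11. That unused tablets could be at hand at an early-termination visit is inferred from the return rule in 8.6.8; it is not a documented event.

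A reader might also suspect damage to the data. The documents do not support that. The week 65 sample is drawn before any tablet, so the measured level would be unaffected, and it remains reasonable as a washout value. No primary or key secondary analysis changes. Correcting the text is optional but worthwhile: it costs almost nothing, and a protocol should not tell sites to dose patients who are off drug.

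**What to change.** 1. In 8.2.7, delete the instruction to take the tablet and record the time, so that Visit 11 is a blood sample only.
2. In 8.2.6, limit the dosing clause to patients still on study treatment at that visit. Early-termination patients who have stopped the drug give the sample and take no dose.
3. As an optional clarification, state in 9.8 and in footnote 3 of Table 1 that the sample-before-dose rule applies only while the patient is on treatment.

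The two necessary edits and the two optional ones can go into the next approved amendment under 13.4. They add no procedure, data item or patient burden, and the week 65 sample is kept.

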8.3 Unscheduled Visit

An unscheduled visit may be performed at any time during the study at the subject's request or as deemed necessary by the investigator. The date and reason for the unscheduled visit will be recorded in the subject's source documents and eCRF.

The reasons for the unscheduled visit could include (but are not limited to):

- Appearance of a new AE or an AE follow-up.
- Change in concomitant medications.
- Laboratory follow-up.
- IMP dispensing, accountability and/or replacement after calling the IWRS to obtain medication kit number.

Protocol No: 005 ARREST study CONFIDENTIAL *Final*

- Subject compliance.
- Other, specify.

It is mandatory to take or collect the following information in each visit:

- Vital Signs.
- Adverse Event.
- Changes in concomitant medication.
- Additional analyses may be performed by the investigator and stated in the source documentation.

8.4 Early Termination

An early termination visit should be completed for all subjects who have been randomized and prematurely discontinue from the study drug.

Every attempt should be made to have subjects return to the clinic for their Early Termination Visit. In case of early termination due to ongoing AE, manifestation of a severe degree of intolerance to IMP and/or disease worsening, the subject should remain under medical observation and followed until the medical condition returns to baseline or is considered stable or chronic.

